15.2 Safety laboratory investigations

Clinical safety laboratory tests will be performed at the times indicated in the schedule of assessments ([Table 3](#)).

Given that this is an acute treatment situation, existing local or locally obtained laboratory values obtained within 48 hours of randomization can be used to assess patient eligibility. However, all laboratory samples required in this trial will be sent to the central laboratory. Results will be available to the investigator within 1-3 days. The investigator is free to use local laboratory values for urgent treatment decisions. Reference ranges must be supplied by the local laboratory and used to assess the laboratory data for clinical significance.

All laboratory samples sent to the central laboratory must be clearly and fully labeled according to the central laboratory manual. The laboratory reports received from the central laboratory via email or fax will be printed, reviewed, signed, and dated by the investigator, and filed at the center. The laboratory results will be additionally imported into the eCRF.

Abnormal results will be assessed by the investigator and classified as clinically significant (yes/no). Clinically significantly abnormal values must be reported as AE, if not already clinically significantly abnormal at Baseline (i.e., pre-dose on Day 0) or if there are known circumstances unrelated to a disease or the medication (such as patient activities or sample handling) that are a likely explanation for the abnormal value.

Persistent clinically significant abnormal values must be followed up using local laboratory values until the cause is determined or until they returned to normal or to the level observed at Baseline (for follow-up of clinically significant laboratory values reported as AEs, see Section [15.1.5](#)).

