9.3 Exclusion criteria

A patient will not be eligible for inclusion if any of the following criteria applies:

Underlying disease-related exclusion criteria

1. Involvement in the trial is not in the patient's best interest according to the investigator's decision, including the presence of any condition that would, in the assessment of the investigator, not allow the protocol to be followed safely

Note: The investigator should particularly consider exclusion of patients at increased risk for serious or fatal AEs in case of worsening of the pulmonary perfusion. This includes, but is not limited to, pre-existing pulmonary hypertension, severe chronic respiratory disease, severely increased risk for thromboembolic complications and moderate to severe left ventricular ejection fraction (LVEF) dysfunction. In addition, other known risk factors of highest risk of mortality in COVID-19 patients should be considered.

2. Presence of respiratory failure, shock, and/or combined failure of other organs that requires ICU monitoring in the near foreseeable future
3. Critical patients whose expected survival time <48-72 hours
4. Presence of the following laboratory values at screening:
 - White blood cell count (WBC) <1.0 x 10⁹/L
 - Platelet count <100,000/mm³ (<100 x 10⁹/L)
 - Total bilirubin >2 x ULN
 - Alanine aminotransferase (ALT) or gamma glutamyl transferase (GGT) >5 x ULN
5. Participation in any other interventional clinical trial
6. Hospitalization primarily for reasons other than COVID-19 (including primarily for concomitant conditions during ongoing SARS-CoV-2 infection)
7. Anticipated transport to a different hospital or institution, in particular when such transport is anticipated for pending ECMO or RRT treatment
8. Clinical suspicion of a bacterial superinfection at Screening

IMP-related exclusion criteria

9. Patients who cannot take drugs orally

10. Allergic or hypersensitive to the IMP or any of the ingredients
11. Use of the following concomitant medications is prohibited from Screening to end of treatment with IMP in this trial (up to Day 14) if not indicated otherwise in this protocol:
 - Concurrent use of any mycophenolate mofetil or of methotrexate exceeding 17.5 mg weekly
 - Any medication known to significantly increase urinary elimination of uric acid, in particular lesinurad (ZurampicTM) as well as uricosuric drugs such as probenecid

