15.1 Adverse events documentation and reporting

15.1.1 Definitions

15.1.1.1 Adverse events

An AE is any untoward medical occurrence in a patient or clinical investigation subject administered a pharmaceutical product, which does not necessarily have a causal relationship with this treatment. An AE can therefore be any unfavorable and unintended sign (including an abnormal laboratory finding), symptom, or disease temporally associated with the use of the IMP, whether or not related to the IMP.

Overdosing, defined as intake of more than twice the intended dose, will not be considered an AE but must be documented as protocol deviation. However, symptoms associated with overdose are considered adverse drug reactions (ADR, for definition see below).

Untoward medical experiences occurring during pre-treatment periods do not meet the above-mentioned definition of AE. Nevertheless, they have to be documented in the same way as AEs, if they occur in the safety monitoring period, i.e., between signing the informed consent form and completion of the EoS visit. Should they already be present at Screening and don't worsen later on, they will only be documented as medical history.

A surgery or procedure scheduled to occur during the trial will not be considered an AE if the surgery or procedure will be performed for a pre-existing condition and the surgery or procedure was planned prior to trial entry. However, if the pre-existing condition deteriorates unexpectedly during the trial (e.g., surgery performed earlier than planned), then the deterioration of the condition for which the surgery or procedure is being done will be considered an AE.

Diagnostic medical or non-surgical procedures will not be considered as AEs. Hospital admission for social, quarantine or convenience reasons will also not be recorded as AE.

AEs that occur between signing the informed consent form and the time when the patient first administers the IMP (Day 0) are defined as pre-treatment AEs.

Treatment-emergent adverse events are defined as any event not yet present prior to the first intake of IMP or any event already present that worsens in either intensity or frequency following exposure to the IMP.

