15.2.2 Blood chemistry, hematology, and coagulation

Blood chemistry, hematology and coagulation assessments will be performed as scheduled in [Table 3](#). For more details on assessments, storage and shipment conditions please refer to [Appendix 1](#).

Abnormal results will be classified as clinically significant (yes/no). Clinically significantly abnormal values, which were not clinically significantly abnormal at Screening, must be reported as AE.

Blood samples will be collected, handled and stored according to the instructions provided by the central laboratory (or local laboratory if applicable). Coagulation samples will be collected and stored at at least -20°C at the site and shipped within 6 weeks to the central laboratory for analysis. Dry ice shipments may be delayed for up to 2 weeks if another patient is expected to finish the respective visit.

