15.2.3 Urinalysis

Urine assessments will be performed as scheduled in [Table 3](#). For more details an assessments, storage and shipment conditions please refer to [Appendix 1](#).

Urinalysis will be done centrally (see [Section 6](#)). Abnormal results will be classified as clinically significant (yes/no). Clinically significantly abnormal values must be reported as AE, if not already clinically significantly abnormal at Screening.

The handling and collection of urine samples will be detailed in the Laboratory Manual.

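### Laboratory AE rule (15.2, 15.2.2, 15.2.3): artefacts are worded as a reason to report, worsening from an abnormal Baseline has no trigger, and the reference visit differs

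*Combined protocol and SAP*

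**What the plan says.** Section 15.2 starts from a binary judgement: "Abnormal results will be assessed by the investigator and classified as clinically significant (yes/no". The AE rule follows: "Clinically significantly abnormal values must be reported as AE, if not already clinically significantly abnormal at Baseline (i.e., pre-dose on Day 0". The same sentence continues "or if there are known circumstances unrelated to a disease or the medication (such as patient activities or sample handling", and closes by saying that these circumstances are a likely explanation of the value.

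Two subsections give their own versions. Section 15.2.2, for blood tests, says "Clinically significantly abnormal values, which were not clinically significantly abnormal at Screening, must be reported as AE". Section 15.2.3, for urine, says "Clinically significantly abnormal values must be reported as AE, if not already clinically significantly abnormal at Screening". Neither mentions artefacts, and both refer to Screening.

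Section 15.1.1.1 gives the general definitions. On AEs it says "An AE can therefore be any unfavorable and unintended sign (including an abnormal laboratory finding". Its definition of a treatment-emergent AE includes "any event already present that worsens in either intensity or frequency following exposure to the IMP".

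Abnormal values at entry are expected. On liver enzymes, exclusion criterion 4 in Section 9.3 removes only "Alanine aminotransferase (ALT) or gamma glutamyl transferase (GGT) >5 x ULN", and on bilirubin only totals above 2 x ULN.

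**The concern.** A site will look to Section 15.2 when deciding whether a laboratory value has to be entered as an AE. It raises three difficulties.

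- **The connective.** *Or if* makes an artefact explanation a second, independent reason to report. The revision history describes the 15.2 change with the same connective, so this is not a fault of text extraction.
- **Worsening.** With a yes/no classification and a test that looks only at whether the value was already significant, a patient who is *yes* on Day 0 and much worse on Day 6 is *yes* both times. The laboratory rule is then silent.
- **The reference visit.** It is pre-dose Day 0 in 15.2 and Screening in 15.2.2 and 15.2.3.

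The matter deserves attention because Section 8.3 names liver and kidney as potential target organs and lists regular liver enzyme monitoring among the risk-minimisation measures. Patients with abnormal entry values are those in whom further deterioration is of most interest. If sites apply different parts of the text, the laboratory AE table will partly reflect which section each site followed.

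**Working it through.** No figure in the plan needs reproducing. The check is one of logic and of comparison between sections.

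**Step 1: the 15.2 sentence as a rule.** Take a post-dose value judged clinically significant. Let B mean that it was already clinically significant at Baseline. Let X mean that a circumstance outside disease and medication probably explains it.

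- As written: an AE is required if (not B) or X.
- With the clause as an exclusion and worsening treated as in 15.1.1.1: an AE is required if (not B, or clinically significantly worse) and not X.

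| B: significant at Baseline | X: artefact likely | 15.2 as written | Exclusion plus worsening |
|---|---|---|---|
| No | No | Required | Required |
| No | Yes | Required | Not required |
| Yes | Yes | Required | Not required |
| Yes | No | Not required, even if worse | Required if worse |

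The two readings agree in the first row, and in the last row when nothing has worsened. They differ in both artefact rows and for genuine worsening.

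**Step 2: two illustrative records** (values chosen for illustration).

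- ALT 4 x ULN and clinically significant on Day 0, which the 5 x ULN entry limit permits; 15 x ULN on Day 6; no artefact. B is true and X is false, so 15.2 does not require an AE.
- Potassium clinically significant on Day 0 and again on Day 6, the second result explained by a spoiled sample. X is true, so 15.2 requires an AE.

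**Step 3: the rules side by side.**

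| Section | Reference point | Worsening covered | Artefact clause |
|---|---|---|---|
| 15.2, all laboratory tests | Baseline, pre-dose Day 0 | No | Yes, as a reason to report |
| 15.2.2, blood | Screening | No | None |
| 15.2.3, urine | Screening | No | None |
| 15.1.1.1, treatment-emergent AE | First IMP intake | Yes | None |
| 15.3, ECG | Screening | Yes, any clinically significant change | None |

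**Step 4: is there a Screening value to compare with?** Section 15.2.4 and Appendix 2 list the local screening tests, and urinalysis is in neither list. Table 3 first schedules it pre-dose on Day 0. Section 15.2.3 therefore points to a reference value that the plan does not require anyone to collect. The coagulation tests covered by 15.2.2 are also absent from both lists. Where a screening value does exist, it comes from a local laboratory, while on-study samples go to the central one.

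**The case against.** The best counter-argument is that the protocol as a whole does capture worsening, and much of it stands.

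- Section 15.2 says *if*, not *only if*. It states when reporting is mandatory and does not forbid recording other values. A reader might infer that worsening from an abnormal baseline is barred from the AE record; the text does not say that.
- Section 15.1.1.1 accepts abnormal laboratory findings as AEs. It leaves conditions present at Screening as medical history only when they do not get worse. Section 15.1.3 requires all AEs to be recorded and names laboratory tests as one way of detecting them. Section 15.1.6 adds laboratory changes, but only those unusual for COVID-19 for which a drug relationship cannot be ruled out.
- A reader might also infer that the stopping criteria in Section 20.1 would undercount. That link is weak. Section 15.1.1.3 ties an SAE to the AE definition in 15.1.1.1, not to the sentence in 15.2.
- The data are kept. Central results are loaded into the eCRF, laboratory parameters are a safety endpoint in their own right, and 15.2 has persistent significant values followed up.
- The artefact clause is an evident slip that many sites would read as intended, and there is no reason to expect its noise to favour one arm.

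What remains is that a specific instruction and the general definitions give different answers for the same record. Section 15.1.6 does not close the gap, because a rise judged usual for COVID-19 falls outside it.

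**Conclusion.** The point holds as a wording fault in an operative safety-reporting rule. Followed literally, 15.2 requires AEs for artefacts and does not itself require one for genuine worsening from an abnormal Baseline. Sections 15.2.2 and 15.2.3 share the second gap and use a different reference visit, which for urine has no required value.

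The consequence is inconsistent recording of laboratory AEs between sites. It is not loss of laboratory data, and it does not show that worsening goes unrecorded across the trial.

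The size cannot be quantified from the documents. A reader might take an assumed 10 to 30% of patients with a significant Day 0 value and compute 200 x 0.10 = 20 to 200 x 0.30 = 60. That would count abnormal baselines at an assumed rate, not missed AEs. The documents give no rate of abnormal baselines, of later worsening, or of sites reading 15.2 literally. The verdict rests on the wording alone and needs none of these.

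**What to change.** Use one rule in 15.2, 15.2.2 and 15.2.3, with pre-dose Day 0 as the only reference. In substance: a clinically significant laboratory abnormality is reported as an AE when it is new, or has worsened to a clinically significant degree, relative to the pre-dose Day 0 value, unless something other than disease or medication (for example patient activity or the handling of the sample) probably accounts for it. Add that the rule is to be read with 15.1.1.1 and remains subject to 15.1.6 for anticipated COVID-19 events.

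This turns the artefact clause into an exclusion, supplies the worsening trigger, and removes the mismatch between Baseline and Screening.

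The cost is one sentence in three sections and a short note to sites. The only downside is a few more laboratory AEs to record in patients who enter with abnormal values.

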15.2.1 Pregnancy tests

Female patients of childbearing potential, i.e., not postmenopausal (where postmenopausal state is defined as no menses for 12 months without an alternative medical cause) or not surgically sterile, must have a local negative pregnancy test before the first intake of the IMP. A blood pregnancy test is required at Screening. Any local urine pregnancy test must be followed up with a confirmatory local blood pregnancy test.

For follow-up procedures in case of pregnancy see Section [15.1.8](#).

15.2.2 Blood chemistry, hematology, and coagulation

Blood chemistry, hematology and coagulation assessments will be performed as scheduled in [Table 3](#). For more details on assessments, storage and shipment conditions please refer to [Appendix 1](#).

Abnormal results will be classified as clinically significant (yes/no). Clinically significantly abnormal values, which were not clinically significantly abnormal at Screening, must be reported as AE.

Blood samples will be collected, handled and stored according to the instructions provided by the central laboratory (or local laboratory if applicable). Coagulation samples will be collected and stored at at least -20°C at the site and shipped within 6 weeks to the central laboratory for analysis. Dry ice shipments may be delayed for up to 2 weeks if another patient is expected to finish the respective visit.

15.2.3 Urinalysis

Urine assessments will be performed as scheduled in [Table 3](#). For more details an assessments, storage and shipment conditions please refer to [Appendix 1](#).

Urinalysis will be done centrally (see [Section 6](#)). Abnormal results will be classified as clinically significant (yes/no). Clinically significantly abnormal values must be reported as AE, if not already clinically significantly abnormal at Screening.

The handling and collection of urine samples will be detailed in the Laboratory Manual.

15.2.4 Screening laboratory

For screening local laboratory test will be used, these should include:

- Positive SARS-CoV-2 test (done locally or obtained within 4 days before randomization by another laboratory)
- Negative blood pregnancy test
- Hematology and blood biochemistry: white blood cell count, platelet count, total bilirubin, ALT, and GGT

15.3 Vital signs, physical examination, and ECG

Vital signs, routine physical examinations, and ECG will be performed as scheduled in [Table 3](#).

Vital signs

Vital signs will include height and weight (both only at Screening), body temperature (°C), pulse rates, systolic and diastolic blood pressures. Height in centimeters and weight in kilograms will be recorded without shoes.

Blood pressure (systolic and diastolic), and pulse must be measured with the patient in a seated position (if possible), after at least 5 minutes at rest.

Body temperature can be measured axillary, oral, rectal or tympanic, but should always be measured by the same method for a patient.

Changes in vital signs judged by the investigator as clinically significant will be reported as an AE.

Physical examination

Physical examinations will cover the following body systems: general appearance, skin, neck (including thyroid), throat, lungs, heart, abdomen, back, lymph nodes, extremities, vascular, neurological systems, and, if applicable, others.

Any new clinically significant finding compared to Screening must be documented as AE.

Any clinically significant finding at Screening Visit 1 must be documented in the medical history section of the eCRF.

12-lead electrocardiogram

The 12-lead ECG (I, II, III, aVR, aVL, aVF, V₁-V₆) will be recorded in supine position after at least 5 minutes at rest (if applicable) using the local standard ECG machine. The ECG will be analyzed qualitatively (normal or abnormal, if abnormal clinically significant [yes/no]). The heart rate, PQ-, QRS-, and QT-intervals, as well as the heart rate-corrected QT_c interval (according to Bazett's formula) will be determined. All procedures will be done according to local practice. Any findings from ECGs collected after the IMP administration will be captured as AEs if, in the opinion of the investigator, there was a clinically significant change from Screening.

16 Biostatistical methods

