Efficacy (continued)	
 • Proportion of patients 
 • with auxiliary oxygen therapy* (including all types of oxygen therapy) until Days 6, 14, and 28 • with clinical recovery defined as 
 • Axillary temperature ≤ 36.6 °C, or oral temperature ≤ 37.2 °C, or rectal or tympanic temperature ≤ 37.8 °C; and • Respiratory frequency ≤ 24 times/min without oxygen inhalation; and • Oxygen saturation $\geq 98\%$ without oxygen inhalation • With clinical improvement, defined as an improvement of at least 2 points on the WHO 9 category ordinal scale [21], or live discharge from hospital without oxygen supplementation, whichever comes first • Change in daily clinical patient status on the WHO 9-category ordinal scale [21] • Duration of INV • Duration of ECMO • Duration of RRT • Duration of auxiliary oxygen therapy (including all types of oxygen therapy) • Duration of hospitalization for survivors • Rate of ICU* admission until Days 6, 14, and 28 • Hospital-free days

Trial objectives and endpoints (continued)

Objective	Endpoint
Secondary (continued)	
Efficacy (continued)	
	
 • Time from IMP treatment initiation to death • Time to first prescription of INV • Time to first prescription of RRT • Time to first prescription of ECMO • Time to first prescription of INV, RRT, and ECMO • Time to ICU admission • Cumulative dose of vasoactive therapies and days (daily until Day 14) with vasoactive therapies (until Day 14) • Time to clinical recovery
Pharmacokinetics	
To evaluate trough plasma levels of IMU-838	
 • Morning trough plasma levels of IMU-838 on Days 0, 1 through 6, 14, and 28 • Correlation of trough levels (quartiles) to selected clinical outcomes
Safety	
To evaluate safety and tolerability of IMU-838	
 • AEs and SAEs • Vital signs • Clinical laboratory parameters (blood chemistry, hematology, and urinalysis) • Electrocardiogram (ECG) parameters • Temperature

Trial objectives and endpoints (continued)

Objective	Endpoint
Secondary (continued)	
Disease markers	
To explore blood levels of disease markers	
 • D-dimer • Lactate dehydrogenase (LDH) • C-reactive protein (CRP) • Troponin I (cTn) • Procalcitonin (PCT) • Correlation of disease markers to selected clinical outcomes

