8.1 Overall trial design

The trial consists of 2 independent parts: a Phase 2 proof-of-activity phase (Part 1) with the option to continue enrollment (without interruption) to a confirmatory Phase 3 part (Expansion Phase, Part 2). Part 2 will only be started after results from main analysis of Part 1 (MA1) has been analyzed and results indicate activity of IMU-838 in COVID-19.

Both parts follow a multicenter, double-blind, placebo-controlled, randomized, parallel-group design to evaluate the safety and efficacy of IMU-838 as addition to investigator's choice of SoC treatment in patients with COVID-19. Eligible patients will be centrally randomized 1:1 to twice-daily (BID) oral 22.5 mg IMU-838 (45 mg/day + SoC) or placebo (+ SoC). Randomization will be stratified by age (< or \geq 65 years) and antiviral therapy (no antivirals, Hydroxychloroquine and Chloroquine, all other antivirals).

Part 1 and Part 2 will be analyzed independently from each other.

The unblinded main analysis of Part 1 (MA1) will be performed after approximately 200 patients have completed Day 28/EoS, either as scheduled or prematurely, while enrollment continues. Based on the MA1 results the trial may be expanded into Part 2, if activity of IMU-838 is observed, or stopped, if no activity of IMU-838 or safety issues are observed. A further 30 patients are expected to be enrolled and treated in a double-blind manner until the results of the MA1 are available (when no activity of IMU-838 was found) or until the enrollment in Part 2 has commenced (if MA1 indicated proof-of-activity). A final analysis of Part 1 (FA1) will be performed after completion of Part 1, using all enrolled patients, i.e. about 230 patients.

In addition, an early safety analysis will be performed and evaluated by an Independent Data Monitoring Committee (IDMC) after 30 patients in Part 1 have completed Day 28 to assess unblinded safety data.

For US centers only: Enrollment into the trial will be paused after these 30 patients have reached Day 28 until the IDMC has evaluated safety stopping criteria. If the trial safety stopping criteria are not fulfilled, the enrollment in the trial will be resumed and the IDMC will continue with a full review of the available safety data.

Further safety analyses can be initiated at any time by the IDMC or Sponsor when new safety signals are identified within this or other trials of IMU-838.

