9.2 Inclusion criteria

1. Male or female patients at least 18 years old (may only be extended to include children 12 years or older after MA1 following approval of a protocol amendment)
2. Admitted to the hospital or other medical in-patient treatment facility for treatment of COVID-19

The hospitalization needs to be for medical reasons (treatment of COVID-19 disease) and cannot be for social reasons or due to housing insecurity.

For US sites only: If the investigator would commonly hospitalize the patient but for healthcare resource reasons decides to treat the patient in a specially designed out-patient setting, then such patients are also allowed to enter the trial (please note that in this case the patient would be counted as clinical status category 3). The investigator then must assure that the patient has at least a twice daily assessment by qualified trial personnel and all laboratory assessments can be adequately performed as per protocol. The Sponsor reserves the right to discontinue this option via administrative letter if such assurances cannot be met by any site.

3. SARS-CoV-2 infection confirmed by reverse transcriptase polymerase chain reaction (RT-PCR) test in a nasopharyngeal, oropharyngeal or respiratory sample at ≤ 4 days before randomization
4. Moderate COVID-19 disease defined as fulfilling clinical status category 3 or 4 on the WHO 9-point ordinal scale [21]:
 - Category 3: Hospitalized (see note above for US only), virus-positive, no oxygen therapy with the following condition:
 - The hospitalization needs to be for medical reasons (treatment of COVID-19 disease) and cannot be for social reasons or due to housing insecurity
 - Category 4: Hospitalized, virus-positive, oxygen by mask or nasal prongs (excluding high-flow oxygen therapy) with the following conditions:

- Peripheral capillary oxyhemoglobin saturation (SpO_2) >92% at maximum of 6 liters oxygen flow per minute
- Stable respiratory rate ≤ 30 breaths/min at maximum of 6 liters oxygen flow per minute

5. Presence of at least 1 symptom characteristic for COVID-19 disease i.e., fever, cough or respiratory distress

6. Willingness and ability to comply with the protocol

7. Written informed consent given prior to any trial-related procedure

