16.3 Statistical analyses

16.3.1 General approaches

For qualitative variables, the frequencies (absolute and relative) will be calculated. Quantitative parameters will be described by declaring the mean value, standard deviation, minimum, first quartile, median, third quartile, and maximum. The treatment groups will be separately tabulated. A detailed description of the statistical analyses for all scheduled analyses (i.e., early safety analysis, MA1 and FA1, and interim and FA2) will be provided in a statistical analysis plan and will be finalized before the respective data (e.g. MA1/FA1, IA2, FA2) will be analyzed.

In Part 1, all endpoints will be analyzed descriptively. In addition, exploratory confidence intervals will be calculated for the primary and key secondary endpoints (and for other endpoints as appropriate) using an alpha of 0.1 (2-sided). No formal statistical tests will be conducted.

The Part 2 (Phase 3 Expansion Phase) trial will be designed to keep a global 1-sided alpha level of 0.025 (1-sided). A 2-stage group sequential test adaptive design with O'Brien and Fleming shaped boundaries will be used. Stage 1 will be the IA applying an overall information rate of 50% and using an alpha of 0.0026. The use of group sequential boundaries within the context of an adaptive design is enabled using the inverse normal method, combining the p-values of both stages with weights based on the sample sizes. Statistical analysis methods that control for the Type I error will be used.

In Part 2, the primary and key secondary endpoints will be tested confirmatory. Results of other endpoints will be considered exploratory, even when statistical tests are performed.

Confirmatory hypothesis testing of key secondary endpoints will be done only after the test of the primary efficacy endpoint was significant. Testing will be done strictly hierarchically in the given order to ensure the family wise error rate. Confirmatory hypothesis testing in the pre-defined order will stop once the first non-significant test result is obtained.

The FAS (all randomized patients who received at least one dose of IMP; as randomized) will be the primary analysis population. The PP analysis set and the set of only surviving patients until EoS will be applied as secondary/sensitivity analysis for the primary and key secondary endpoints, if applicable.

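### Bazett is the only QT correction named in Section 15.3, so any change in heart rate between baseline and later ECGs moves QTc without a change in repolarization; Fridericia can be derived from data already recorded

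*Combined protocol and SAP*

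**What the plan says.** Section 15.3 has a 12-lead ECG recorded supine after rest, if applicable, on the site's own machine. It lists the quantities to be obtained as "The heart rate, PQ-, QRS-, and QT-intervals" together with a rate-corrected QTc, which "interval (according to Bazett's formula) will be determined". It adds that "All procedures will be done according to local practice". No second correction appears anywhere in the document.

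Section 7 lists "Electrocardiogram (ECG) parameters" among the safety endpoints. The ECG row of Table 3 (Section 12.1), whose layout is partly lost in the available text, reads as Day 0 before and after dosing, then Days 3, 6, 14 and 28.

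Under Section 15.3, an ECG finding after dosing is captured as an adverse event if, in the investigator's opinion, "there was a clinically significant change from Screening". For the group analysis, Section 16.3.1 gives general descriptive statistics and states that "The treatment groups will be separately tabulated". It leaves the detail to a statistical analysis plan to be finalized before each analysis. The protocol sets no QTc threshold and specifies no QTc change-from-baseline or between-arm QTc analysis.

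**The concern.** Bazett divides QT by the square root of the RR interval. If QT in fact follows RR with a smaller exponent, Bazett over-corrects at high heart rates. A patient whose heart rate falls from entry to a later visit then shows a shorter QTc with no electrical change, and one whose heart rate rises shows a longer one.

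This matters here because the baseline ECG is taken early in an acute illness. Section 8.1 encourages screening and randomization on the day of hospitalization, and Section 15.1.6 gives fever, dyspnea, viral pneumonia and hypoxia as typical baseline symptoms. Later ECGs fall in recovery or deterioration, so some change in heart rate is plausible in either direction.

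Two uses of the ECG are exposed. One is the site-level adverse event judgement, which sets a patient against that patient's own earlier ECG and has no placebo correction. The other is any summary of change from baseline read within one arm.

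**Working it through.** **Inputs from the documents.** Section 15.3 supplies the correction (Bazett only) and confirms that heart rate and uncorrected QT are both determined. Sections 8.1 and 16.3.1 supply 1:1 placebo control and tabulation by group. The protocol states no QTc figure, so there is none to reproduce.

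**Assumptions, not document figures.** Baseline heart rate 80 to 110 beats/min, later heart rate 65 to 80, and true Fridericia QTc constant at 400 or 420 ms.

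**Formulas.** With RR = 60/HR in seconds:

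- Bazett: QTcB = QT / (60/HR)^(1/2)
- Fridericia: QTcF = QT / (60/HR)^(1/3)
- Hence QTcB = QTcF × (HR/60)^(1/6)

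**Step 1: change within a patient, no true effect.** Changes are taken before rounding.

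| QTcF held at (ms) | Heart rate (beats/min) | QTcB (ms) | Artificial change (ms) |
|---|---|---|---|
| 400 | 80 to 75 | 419.6 to 415.2 | −4.5 |
| 400 | 90 to 75 | 428.0 to 415.2 | −12.8 |
| 400 | 100 to 75 | 435.5 to 415.2 | −20.4 |
| 420 | 100 to 75 | 457.3 to 435.9 | −21.4 |
| 420 | 110 to 65 | 464.6 to 425.6 | −39.0 |

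The first and last rows are the extremes over the assumed range. Reversing the heart-rate course reverses the sign: 75 to 100 beats/min at 400 ms gives a false prolongation of 20.4 ms.

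**Step 2: change within a patient, true effect of +20 ms.** At 100 to 75 beats/min from QTcF 400, follow-up QTcB is 420 × (75/60)^(1/6) = 435.9 ms against 435.5 ms at baseline. The reading is +0.4 ms, so the effect is hidden.

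**Step 3: between arms, same heart-rate course.** In the same case active changes by +0.4 ms and placebo by −20.4 ms. The difference is +20.8 ms, so the +20 ms effect survives. A true +10 ms effect reads as +10.4 ms.

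**Step 4: between arms, different heart rate at follow-up.** Placebo is at 75 beats/min, with QTcF 400 on placebo.

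| Active heart rate (beats/min) | No true effect: QTcB difference (ms) | True +10 ms: QTcB difference (ms) |
|---|---|---|
| 70 (5 lower) | −4.7 | +5.5 |
| 75 (equal) | 0.0 | +10.4 |
| 80 (5 higher) | +4.5 | +15.0 |

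With no true effect, 4.7/5 and 4.5/5 both give about 0.9, so roughly 1 ms per beat/min in either direction.

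**Step 5: dependence on the true QT-RR relation.** Let QT = 400 × (60/HR)^e, with heart rate going from 100 to 75 beats/min.

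| True exponent e | Bazett change (ms) | Fridericia change (ms) |
|---|---|---|
| 0.25 | −31.5 | −9.9 |
| 1/3 | −20.4 | 0.0 |
| 0.40 | −11.9 | +7.5 |
| 0.50 | 0.0 | +18.0 |

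Fridericia has the smaller error in the first three rows. Bazett is exact only at 0.50.

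**The case against.** **The population.** A reader might infer that the trial enrols febrile, tachycardic patients, so that a large fall in QTc is certain. The documents do not support that. Section 9.2 asks for "Presence of at least 1 symptom characteristic for COVID-19 disease i.e., fever, cough or respiratory distress", so fever is one of three alternatives. There is no heart-rate criterion, disease is moderate, and ECGs follow a rest period where applicable. This objection stands: the size of the artefact is conditional on assumed heart rates.

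**The placebo arm.** A reader might also infer that a fall of 20 ms or more would mask prolongation by IMU-838 in the trial's comparison. Section 8.1 provides that "Eligible patients will be centrally randomized 1:1 to twice-daily (BID) oral 22.5 mg IMU-838" or placebo, double-blind. A recovery effect common to both arms cancels, as Step 3 shows. This stands too. Only a heart-rate difference between arms survives, and it can exaggerate a prolongation as readily as hide one. Masking requires a lower heart rate on IMU-838, for instance through faster recovery, and that is a hypothesis.

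**No rule depends on QTc.** The adverse event rule rests on opinion about any ECG finding, the ECG is also read qualitatively, and no eligibility, activity or trial stopping criterion uses a QTc number. The risk discussion in Section 8.3 reports no QT signal. All of this limits the consequence. It does not make Bazett a sound sole measure for a listed safety endpoint.

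**The analysis plan is still to come, and no raw data are lost.** True, and this is why the remedy is cheap. But the protocol as written names Bazett alone, and a later plan for group tables would not by itself change what the investigator weighs when judging one patient's ECG.

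**Fridericia is not exact either.** Correct, as Step 5 shows. It is a reason to keep both values available.

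**Conclusion.** The point holds in a limited form. Bazett is the only correction named, and it makes QTc depend on heart rate whenever the true QT-RR exponent is below 0.50. For assumed falls between 80 to 75 and 110 to 65 beats/min, with Fridericia QTc constant at 400 to 420 ms, the artificial fall is about 4.5 to 39 ms; a rise in heart rate gives a false prolongation. For 100 to 75 beats/min the fall ranges from 31.5 ms to zero as the exponent goes from 0.25 to 0.50.

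Single-patient and single-arm readings against baseline carry the whole of this distortion. The randomized comparison carries only about 1 ms per beat/min of heart-rate difference between arms, with no fixed direction. The documents therefore support neither a claim that IMU-838 prolongs QT nor a claim that the placebo comparison would miss it. This is a worthwhile refinement of the safety analysis and does not threaten the trial's main conclusions.

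**What to change.** In the statistical analysis plan, derive QTcF = QT / (60/HR)^(1/3) centrally from the QT and heart rate already determined at each ECG. Make it the QTc for the safety tables and for change from baseline, shown by arm with the placebo comparison. Tabulate heart rate by arm at the same visits, so that any residual rate effect can be judged. Keep Bazett as a supplementary listing.

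In Section 15.3, name Fridericia as the correction, so that the site's reading of change within a patient uses the same measure. While that sentence is open, align the reference point: the adverse event rule speaks of Screening, but Table 3 appears to place the first ECG at Day 0 before dosing.

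The cost is one derived variable and a small wording change. No additional ECGs or staff are needed. The downside is that values will be less directly comparable with any earlier Bazett data, which the supplementary listing largely covers.
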